7.0 DRUG FORMULATION AND ADMINISTRATION

7.1 GVAX/Placebo

7.1.1 Description

GVAX is a GM-CSF secreting autologous leukemia cell vaccination.

The vaccine is produced through adenoviral vector mediated GM-CSF gene transfer into myeloblasts harvested from study subjects prior to admission for HSCT. The placebo vaccine will consist of a sterile normal saline solution.

7.1.2 Form

Cells for vaccine will be thawed in a dedicated laminar flow biosafety cabinet in the CMCF and washed. Cells will be resuspended in a volume of 1 ml. for administration.

7.1.3 Storage and Stability

Tumor cells for vaccination and immunologic evaluation will be cryopreserved and stored in liquid nitrogen. Six individual vaccine aliquots will be prepared for each patient. Cell dose per aliquot will be fixed for an individual patient and will range from a minimum of $1x10^6$ cells per aliquot to $1x10^7$ cells per aliquot. The dosage will be determined by dividing the total cell yield following transduction into six aliquots. Thus, a minimum of $6x10^6$ cells will be required to

prepare six aliquots of $1x10^6$ cells. For total cell yields greater than $6x10^7$, individual aliquots will remain at $1x10^7$ cells per dose.

7.1.4 Handling

Qualified personnel, familiar with procedures that minimize undue exposure to themselves and the environment, should undertake the preparation, handling, and safe disposal of the chemotherapeutic agent in a self-contained and protective environment.

7.1.5 Availability

GVAX/Placebo is an investigational agent and will be supplied free-of-charge from CMCF.

7.1.6 Preparation

7.1.6.1 GVAX

Harvested autologous myeloblasts will be transferred to the Cell Manipulation Core Facility (CMCF) at the Dana Farber Cancer Institute. The autologous myeloblasts will be introduced into short-term tumor culture in the presence of G-CSF, and transduced with a replication defective adenoviral vector encoding human GM-CSF.

After transduction, the tumor cells will be washed extensively and irradiated with 10,000 cGy. A radiation indicator tag that changes color from red to black after radiation will be appended to the bag containing the cells to assure that radiation is completed. In addition, the completion of radiation will recorded by 2 qualified members of the laboratory, who will also verify that the appropriate radiation dose of 10,000 cGy is delivered.

A small aliquot of the transduced cells will be placed into culture and GM-CSF secretion will be determined by ELISA. The target level for GM-CSF production will be at least 40 ng/10⁶ cells/24 hours, although achieving this secretion will not be required for vaccine administration. Routine sterility cultures and testing for endotoxin and mycoplasma contamination will be performed.

Tumor cells for vaccination and immunologic evaluation will be cryopreserved and stored in liquid nitrogen. Six individual vaccine aliquots will be prepared for each patient. Cell dose per aliquot will be fixed for an individual patient and will range from about $1x10^6$ cells per aliquot to $1x10^7$ cells per aliquot. The exact vaccine cell dose in each patient will vary depending on the total yield of myeloblasts harvested. Vaccine dose will be calculated based on the myeloblast count performed on a post-ficoll sample assessed in the Hematology Laboratory at DFCI. Following transduction, the final product will be divided equally into six aliquots to yield 6 vaccines of the same dose. For total cell yields greater than $6x10^7$, individual aliquots will remain at a maximum of $1x10^7$ cells per dose.

On the day of vaccination, cells will be thawed in a dedicated laminar flow biosafety cabinet in the CMCF and washed. Cells will be re-suspended in a volume of 1 ml. in a syringe for administration. The syringe will be masked with special tape to prevent administrating personnel from distinguishing cellular vaccines from placebo.

7.1.6.2 Placebo

The placebo vaccine will be prepared by the CMCF staff on the day of vaccination. The vaccine will consist of 1 ml. sterile normal saline. The syringe will be masked with special tape to prevent administrating personnel from distinguishing cellular vaccines from placebo.

7.1.7 Administration

GVAX/Placebo vaccinations will be administered weekly x 3 weeks, then q2weeks x 6 weeks for a total of 6 vaccines. The weekly scheduling of vaccination can be +/- 2 days for scheduling flexibility.

A study team physician, physician assistant, nurse practitioner, registered nurse, or research registered nurse can administer the injections in either an inpatient or outpatient clinic. Injections will be administered according to standard nursing procedure in the patient's arms and thighs on a rotating basis. Injections must be performed without the prior application of EMLA or other topical or local anesthetics, as such compounds both could obscure local reactions to the vaccination and could cause reactions that might be interpreted as vaccine reactions. Approximately 1/2 of the vaccine dose should be administered subcutaneously, and remaining half the vaccine dose intradermally. It is recommended that about half of the vaccine be given first intradermally, and the rest subcutaneously by changing the angle of the needle.

Information regarding the number and location of the injections, the date and time of vaccination, route of administration, total volume of vaccine administered and vaccine site injection reactions will be collected for each vaccination and recorded in the patient's chart.

7.1.8 Ordering

Orders for the collection of cells, manufacturing of vaccine/placebo, and release of the vaccine/placebo will be done through the electronic Biologic Order Entry system, as is standard for all cellular therapy order entry at the DFCI. The GVAX/placebo vaccine will be manufactured at the Cell Manipulation Core Facility(CMCF). Once an order for processing has been received by CMCF, GVAX cells will be thawed or the placebo vaccine will be prepared for administration accordingly.

7.1.9 Accountability

GVAX/placebo accountability is maintained by the Cell Manipulation Core Facility (CMCF).

7.1.10 Destruction and Return

CMCF will receive reagents, if they are not used the reagents will be held for future use until they are out of date at which point they will be destroyed according to institutional policies. Destruction will be documented in the Drug Accountability Record Form.

8.0 CORRELATIVE/SPECIAL STUDIES

Biologic responses to vaccination following allogeneic stem cell transplant will be assessed by laboratory and histologic analyses of blood before and after vaccination, and skin biopsy samples at vaccination. Bone marrow aspirates will also be cryopreserved, if sufficient material is available. We anticipate that vaccination will elicit robust infiltrates composed of dendritic cells, macrophages, granulocytes, and lymphocytes. The numbers and proportions of CD4+ and CD8+ T effectors and FoxP3+ Tregs will be evaluated. The local production of relevant cytokines and chemokines will also be examined using real-time PCR and commercially available RNase protection assays.

Serum and circulating mononuclear cells will be frozen prior to beginning vaccination and at regular intervals thereafter. These longitudinal samples will be analyzed for immune cell numbers and subsets. We will use multicolor flow cytometry methods (5 or 9 color), already established in the Cancer Vaccine Center Immune Assessment Core, to investigate immune cell subsets. These phenotypic measurements will be complemented with functional studies. An evaluation of T cell proliferation, cytokine production, and cytotoxicity will be undertaken, employing autologous tumors as targets, when available. The samples will also be used in research studies aimed at identifying the target antigens of vaccination, characterizing NK, T and B cell responses to these targets, and delineating the mechanisms involved in protective immunity. These research tests may include evaluation of reactivity to targets identified in earlier vaccine studies; these may include ATP6S1, melanoma-inhibitor of apoptosis protein (ML-IAP), opioid growth factor receptor (OGFr), CML28, CML66, PDI, ERp5, L1CAM, angiopoietin-1/2, MIF, progranulin, and MICA.

9.0 STUDY CALENDAR

Tests/Evaluations	Enrollment	Leukemia	Day 20-30	Vaccine 1	During	1 month*	6 months*	9months*	12 & 18 month*
	Pre-SCT	Cell	post SCT	Day30-609	vaccination	after last	post SCT	post SCT	post SCT
		Harvest		post SCT		vaccine			•
Informed Consent	X								
Physical Exam	X		X	X	Qwk	X	X	X	X
Adverse Event assessment		X	X	X	Qwk	X	X	X	X
GVHD assessment			X	X	Qwk	X	X	X	X
Pre-transplant testing ¹	X								
CBC with differential	X		X	X	Qwk	X	X	X	X
Bun/Cr, LFTs, LDH	X		X	X	Qwk	X	X	X	X
CMCF/Immune Bloods ²	X		X	X	Qmonth	X	X	X	X
Marrow Asp/BX	X ⁴	X ^{5,6}		X ⁵		X ⁵			X ⁵
Peripheral blood leukemia cell harvest		X ⁷							
Vaccine specific toxicity Assessment (Appendix I)				X	Qwk	X			
Skin bx of vaccination ³				X	Vaccine 5				
cGVHD Form (Appendix II)						X8	X8	X8	X ⁸

- 1 Standard pre-transplant testing per institution guidelines
- 2 Approximately 60cc blood
- 3 Skin biopsies of vaccine site(2-3 days after injection) are strongly encouraged, but not required for study participation.
- 4 Should be performed \leq 28 prior to enrollment if the patient has received intervening therapy
- 5 Also sent for flow cytometry, FISH/cytogenetics, chimerism (if post SCT), molecular studies (if applicable). An additional marrow aspirate sample is encouraged, but not required to be drawn during protocol bone marrows, and should only be collected if there is excess marrow aspirate available and a sufficient number of cells for banking by the CMCF.
- 6 Optional if patient qualifies for peripheral blood leukemia cell harvest or at treating physician's discretion if previous restaging marrow aspirate/biopsy was within two weeks of collection.
- If the patient has blasts in peripheral blood, tumor cells may be collected by blood draw. The amount of blood required may vary depending on calculations of blood volume needed to yield a desired target of 2 x 10⁷ leukemia cells. If the calculated volume of blood draw exceeds 50 ml, it is recommended that bone marrow aspiration be used as the method for tumor cell harvest.
- 8 Participants will have cGVHD assessed with the cGVHD form at every protocol visit once the participant has developed cGHVD.
- 9 Day 60 or next business day, if day 60 occurs on a weekend or holiday
- * +/- 2 weeks to allow for scheduling flexibility. Please refer to Section 5.3.5 and 5.3.6 to determine off treatment criteria with continued study visits and those with survival follow-up only.
- ▶ Because this is a gene transfer study, all participants who received at least one vaccination will be followed for safety for up to 15 years after removal from study, or until death, whichever occurs first (see Section 5.6 for additional information).

10.0 ADVERSE EVENT REPORTING REQUIREMENTS

10.1 Definitions

10.1.1 Adverse Event (AE)

An adverse event (AE) is any undesirable sign, symptom or medical condition or experience that develops or worsens in severity after starting the first dose of study treatment or any procedure specified in the protocol, even if the event is not considered to be related to the study.

Abnormal laboratory values or diagnostic test results constitute adverse events only if they induce clinical signs or symptoms or require treatment or further diagnostic tests.

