5.3 GVAX/Placebo Vaccination

Vaccination with GVAX or placebo vaccine will commence after hematologic recovery has occurred and the patient is between day +30 to day +60* post transplant. Vaccine administration can occur on an either inpatient or outpatient basis. At any time between day+30 to day +60*, the patient may undergo a bone marrow aspirate/biopsy and GVAX/placebo vaccination may commence provided the following criteria are satisfied:

* Day 60 or next business day, if day 60 occurs on a weekend or holiday

5.3.1 Criteria for starting GVAX/Placebo administration:

- No grade II-IV acute GVHD
- No systemic corticosteroid therapy*
- No uncontrolled acute infection
- No CTC grade ≥ 3 non-hematologic toxicity
- Absolute neutrophil count $\geq 500/\text{ul}$ off growth factor

- Platelet count ≥ 10 K/ul without transfusion.
- Absolute eosinophil count ≤ 5000/ul

Participants who do not meet the above criteria to start vaccination by day +60 will be considered "off treatment", and followed for survival.

5.3.2 **GVAX/Placebo Administration:**

- 5.3.2.1 Vaccinations will be administered weekly x 3 weeks, then q2weeks x 6 weeks for a total of 6 vaccines. The weekly scheduling of vaccination can be +/- 2 days for scheduling flexibility. A physician, PA, NP, RN, or research RN can administer the injections in either an outpatient or inpatient clinical setting. Injections will be administered according to standard nursing procedure in the patient's arms and thighs on a rotating basis. Injections must be performed without the prior application of EMLA or other topical or local anesthetics, as such compounds both could obscure local reactions to the vaccination and could cause reactions that might be interpreted as vaccine reactions. Approximately half of the vaccine dose should be administered subcutaneously, and remaining half the vaccine dose intradermally. It is suggested that about half of the vaccine be given first intradermally, and the rest subcutaneously by changing that angle of the needle.
- 5.3.2.2 Information regarding the number and location of the injections, the date of vaccination, route of administration, total volume of vaccine administered and vaccine site injection reactions will be collected for each vaccination and recorded in the patient medical record.

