5.3.3 Early discontinuation of GVAX/Placebo vaccination

- 5.3.3.1 Disease relapse or progression requiring taper or withdrawal of tacrolimus, or additional systemic therapy.
- 5.3.3.2 Acute GVHD or chronic GVHD requiring systemic steroid therapy.
- 5.3.3.3 CTC grade ≥ 4 non-hematologic toxicity possibly, probably or definitely related to vaccination.
- 5.3.3.4 Delay of vaccination over 14 days (see below)

^{*} Except for physiologic doses of steroids for adrenal insufficiency

- 5.3.4 **Delay of GVAX/Placebo vaccination**: If severe hematologic toxicity (defined as ANC <500/ul, platelet < 10K/ul, or absolute eosinophil count > 5000/ul), CTC grade ≥ 3 non-hematologic toxicity develops during the vaccination period, vaccination may be delayed up to 14 days until the event has improved by at least 1 CTC grade. If condition is not improved after 14 days in the opinion of the treating physician and/or study PI, or if the toxicity recurs upon reinitiation of vaccination, no further vaccination will be given. In an event where the toxicity is grade < 3, vaccination may also be delayed at the physician's discretion.
- 5.3.5 **Off Treatment Criteria with continued study visits**: Patients who receive at least 1 vaccination, but do not complete 6 vaccines for any reason other than disease relapse requiring additional therapy or hospice will be considered "off treatment". These patients will continue "on study" for study visits, tests/procedures, and assessment of toxicity and survival end points. It is preferred that study specific blood samples be drawn and bone marrow biopsies are performed according to the study calendar, but these may be foregone for clinical reasons or if the patient declines to have one performed.
- 5.3.6 **Off Treatment Criteria with survival follow-up only**: Patients meeting the following criteria will be considered "off treatment" and no further study visits, or study related testing will be performed. Survival information will be recorded.
 - 5.3.6.1 Patients who have disease relapse after starting vaccination and require additional therapy (chemotherapy or immune therapy) or hospice placement.

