 - 6.1.1.3 **Potential for prolonged survival of leukemia vaccine cells**: All GM-CSF transfected autologous vaccine cells used in this trial will be irradiated with 10,000 rads to ensure they will die after several days. It is thus unlikely, but theoretically possible, that some tumor cells can survive the radiation, secrete GM-CSF long-term, or even cause leukemia relapse. These events have not been observed in any of the prior studies using retroviral or adenoviral transfected autologous tumor cell GVAX. However, in another study using a different type of GVAX vaccine composed of K562 leukemia cells transfected with GM-CSF and mixed with autologous tumor cells (DFCI Protocol 08-160), there was one case where the GM-CSF secreting K562 cells persisted at the vaccine site, and resulted in severe eosinophilia that proved to be ultimately fatal. It should be noted that K562 cells are not being used in this trial.
 - 6.1.1.4 **Auto-immune diseases**: This is a theoretic possibility for which patients will be monitored. In principle, the mechanisms that allow the immune system to recognize tumor antigens could also lead to breakdown of tolerance to normal or self-antigens, generating an autoimmune reaction. In the B16 murine melanoma model, vaccination with GM-CSF expressing tumor has been associated with depigmented patches of skin, an indication of tissue-specific autoimmunity. No examples of autoimmunity were seen in previous GVAX trials in AML, melanoma, renal cell carcinoma, prostate cancer, pancreatic cancer and lung cancer.
 - 6.1.1.5 **DMSO toxicity**. This toxicity is unlikely since the vaccine will be washed prior to administration. The cells are cryopreserved in 10% DMSO. DMSO is a hydrophilic

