6.2 Toxicity Management

6.2.1 Vaccine site reaction- Local vaccine site reactions are generally transient and self limiting. Local management may include cold compress, moisturizing lotions. Topical steroids and/or topical antihistamines should be avoided if possible so as to not potentially blunt the

immunologic response to the vaccine. If the reaction persists more than 1 week, or the area of erythema and induration persists, a skin biopsy of the area will be considered.

6.2.2 Severe Eosinophilia- If increased absolute eosinophil count to > 5.0 x10^9/L (5000/ul) occurs during the vaccination period, further vaccines will be delayed (see section 5.3.4). In the event that the absolute eosinophil count remains >5.0 x10^9/L for more than 2 weeks despite being off vaccination, no further vaccinations will be given. Since mild eosinophilia is common after allogeneic HSCT, and is also a well recognized and expected response to vaccine, a transient increase in absolute eosinophil count is not an automatic cause for halting all future vaccinations.

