12.0 STATISTICAL CONSIDERATIONS

12.1 Endpoints

12.1.1 **Primary Endpoint**: The primary endpoint of this study is progression-free survival (PFS) at 18 months post-randomization. Progression-free survival is defined as time from randomization to progression of disease or death whichever occurs first. Patients with relapse/progressive disease who re-enter remission after vaccination or upon withdrawal of immune suppression alone will not be considered as having disease progression. The primary analysis will be performed using the modified intention-to-treat (ITT) principle, i.e., all transplanted and eligible patients who receive at least one vaccination will be included in the analysis according to the treatment arm they are randomized to.

12.1.2 **Secondary Endpoints**

- 12.1.2.1 Safety and toxicity of vaccination, as measured by the development of:
 - Grade II-IV and III-IV acute GVHD
 - CTC grade \geq 3 non-hematologic toxicity, or

- Grade \geq 4 hematologic toxicity attributable to vaccination
- 12.1.2.2 Biologic responses to vaccination following allogeneic stem cell transplant, as assessed by laboratory and histologic analyses of blood before and after vaccination, and skin biopsy samples at vaccination sites (Section 8.0). Serum and circulating mononuclear cells will be frozen prior to beginning vaccination and at regular intervals thereafter. Bone marrow aspirates will also be cryopreserved, if sufficient material is available.

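### An eosinophil count above 5000/ul can hold vaccination, but no rule requires an asymptomatic case to reach the by-arm safety data, and Sections 5.3.4 and 6.2.2 contradict each other on the hold

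*Combined protocol and SAP*

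**What the plan says.** **Eosinophil rules.** Section 5.3.1 lets vaccination start only with "Absolute eosinophil count ≤ 5000/ul". For the vaccination period, Section 5.3.4 names "severe hematologic toxicity (defined as ANC <500/ul, platelet < 10K/ul, or absolute eosinophil count > 5000/ul") and says that "vaccination may be delayed up to 14 days until the event has improved by at least 1 CTC grade". Vaccination ends if the treating physician and/or study PI judges that there is no improvement after 14 days, or if the toxicity returns on restarting. Section 6.2.2 says that a count above the same level which "occurs during the vaccination period, further vaccines will be delayed (see section 5.3.4"). It adds: "In the event that the absolute eosinophil count remains >5.0 x10^9/L for more than 2 weeks despite being off vaccination, no further vaccinations will be" …, so vaccination then stops.

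**Background.** Section 6.1.1.3 reports one case in another study in which GM-CSF secreting cells "persisted at the vaccine site, and resulted in severe eosinophilia that proved to be ultimately fatal". That product contained K562 cells, and the section states that they are not used in this trial.

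**Recording rules.** Section 10.1.1 says: "Abnormal laboratory values or diagnostic test results constitute adverse events only if they induce clinical signs or symptoms or require treatment or further diagnostic tests". Sections 10.2 and 10.3 set the hematologic floor at grade 4. The hematologic part of the safety endpoint in Section 12.1.2.1 is grade 4 or higher "hematologic toxicity attributable to vaccination". Section 12.7 compares the arms on related toxicity of grade 3 and above. Appendix I lists local reactions, five general symptoms and a free-text row for anything else; eosinophils are not named. The study calendar (Section 9.0) schedules a CBC with differential weekly during vaccination, one month after the last vaccine, and at 6, 9, 12 and 18 months post SCT.

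**The concern.** The protocol gives this count the standing of a safety signal: it bars the start of vaccination, it is defined as severe, and it has its own management section. The recording rules do not follow it through. A temporary hold for an asymptomatic, untreated count is not clearly an adverse event, has no named place on the toxicity form, and enters the safety endpoint or interim comparison only after passing filters on grade and attribution.

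At stake is the comparison that the placebo arm makes possible. Section 6.2.2 says that mild eosinophilia is common after HSCT and also expected after vaccine, so a blinded investigator has little basis for attributing a particular rise. The informative summary is the frequency of high counts in each arm without an attribution filter, and no section asks for it.

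The hold rule also depends on the record. Section 5.3.4 ends vaccination if the toxicity returns on restarting, and auditing that decision requires the first hold to be documented. If Sections 5.3.4 and 6.2.2 lead sites to different decisions, the number of vaccines received will vary for reasons unrelated to the patient, and Section 12.8 plans to model that number.

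**Working it through.** The plan states no figure to reproduce on this point. The check is a unit conversion and a comparison of sections.

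**1. Do the sections use one threshold?** Sections 5.3.1 and 5.3.4 use 5000/ul; Section 6.2.2 uses 5.0 x 10^9/L. With 10^6 ul per litre, 5.0 x 10^9 / 10^6 = 5000/ul. The threshold agrees, so any conflict lies in the rules attached to it.

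**2. Follow one event through the recording rules.** Take a patient in the vaccination period with a count above 5000/ul, no symptoms and no treatment, whose dose is held and whose vaccination then resumes.

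| Place | Condition for capture | Is capture required? |
|---|---|---|
| 10.1.1 | Signs or symptoms, treatment, or further tests | Not clearly: a held dose is not a listed trigger |
| 6.0 | All AEs from first vaccination, no grade floor | Only if 10.1.1 already makes it an AE |
| 10.2, 10.3 | Hematologic grade 4 or higher (10.3: any attribution) | Depends on a CTC grade not given in the documents |
| 12.1.2.1 | Hematologic grade 4 or higher and attributable | Depends on grade and attribution |
| 12.7 | Grade 3 or higher and related | Depends on grade and attribution |
| Appendix I | No eosinophil row; free-text row | Optional |
| 11.1.2 | Off-treatment form when treatment stops | No: a temporary hold does not trigger it |

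Every route either carries a condition that this event may fail or is optional. The laboratory value exists in each case, because the differential is scheduled weekly.

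**3. Set the hold rules side by side.**

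| Question | Section 5.3.4 | Section 6.2.2 |
|---|---|---|
| Is the hold mandatory? | No, vaccination *may* be delayed | Yes, it *will* be delayed |
| What is measured? | Improvement by at least one CTC grade | The count against 5.0 x 10^9/L |
| What ends vaccination? | No improvement after 14 days, or recurrence on restarting | Count still above the limit for more than 2 weeks off vaccine |
| Who or what decides? | Opinion of treating physician and/or PI | The count |

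Now take a patient whose count has fallen, and is judged improved, but is still above 5000/ul when the two weeks run out. Section 5.3.4 allows vaccination to resume. Under Section 6.2.2 the hold continues and, once two weeks are exceeded, vaccination ends.

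Section 5.3.3.4 separately makes a delay of more than 14 days a reason to stop. That confines the disagreement to the decision at or before 14 days but does not remove it: one section lets the next dose be given while the other withholds it and so runs the patient past the limit. Section 6.3 refers readers to Sections 5.3.3 and 5.3.4 for delay and discontinuation and does not mention 6.2.2.

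**The case against.** The strongest reply is that the event will usually leave a trace. The weekly differential generates the value. Section 5.3.2.2 requires the date of each vaccination in the medical record, so a delay shows against the schedule. Appendix I has a free-text row with grade and attribution columns, and a permanent stop produces an off-treatment form. Section 11.1.2 lists its forms as additions to the transplant repository data, whose forms are not available here. The DSMB may ask for laboratory values (Section 11.2). All of this stands, so a reader who inferred that the event goes unrecorded would be going too far. What is missing is a requirement to capture it as safety data and compare it by arm.

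A second reply is that repeat counts during a hold are further diagnostic tests, which would make the event an AE under Section 10.1.1. That reading is open, but the counts are already scheduled weekly, so sites could reasonably differ. An explicit rule would settle it.

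A third is that CTCAE version 5.0 may grade such a count high enough to pass the filters. The documents do not reproduce that grading, so a miss at grade 3 or 4 can be neither shown nor excluded. The attribution filter in Sections 12.1.2.1 and 12.7 remains either way.

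On the hold, Section 6.2.2 cross-refers to 5.3.4 and both use a two-week limit. They overlap, but that does not settle *may* against *will*, or grade against count.

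**Conclusion.** Two points hold. First, no section requires an asymptomatic, untreated count above 5000/ul that only holds a dose to be captured as an AE, a named form item or a safety endpoint event, so an excess in one arm could be missed. Second, Sections 5.3.4 and 6.2.2 contradict each other and can give opposite decisions for the same patient. This review takes no position on which rule is right.

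The size of the first point cannot be given: the documents state no rate for such counts, and any number of missed cases would be invented. The conclusion assumes that the repository forms and the Manual of Procedures, neither of which is available here, do not already require the item.

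Three stronger inferences are not supported:

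- *That eosinophilia is the only route to death the protocol names.* Section 6.1.1.9 says prolonged pancytopenia after transplant may be fatal. The cited eosinophilia death involved a K562-based product not used here, and Section 6.1.1.3 says such events were not seen in prior studies of retroviral or adenoviral autologous GVAX.
- *That counts after the sixth vaccine have no reporting consequence.* AE reporting runs to 18 months post SCT (Sections 6.0 and 10.3), so a late rise that meets the AE definition is covered. The late gap is again limited to asymptomatic, untreated counts.
- *That every such count needs an expedited report.* Nothing in the documents makes this necessary; it would be a preference.

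**What to change.** 1. Reconcile Sections 5.3.4 and 6.2.2, read with 5.3.3.4, into one rule for hold, resumption and stop, with the sponsor deciding its content. Make Section 6.3 point to it.
2. Add two fields to Appendix I: peak absolute eosinophil count since the last form, and dose held with reason.
3. Tabulate patients with a count above 5000/ul by arm, regardless of symptoms, CTC grade or attribution, in the DSMB safety tables and the final safety analysis. Later counts can come from the differentials already scheduled to 18 months.

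The cost is a text edit, two form fields and one table row. No extra blood draw and no change to sample size, threshold or reporting timeline is needed. The downside is that some transient eosinophilia will be listed; the 5000/ul cut-off limits this, and the comparison with placebo puts it in context.
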